### 3.10.3. Prior and Concomitant Medication

When tabulating prior/concomitant medication data, partial start dates will be handled as follows:

- If the year, month, and day are all missing, then set the start date to the date of first dose.
- If the month and day are missing and the year is earlier than the year of the first dose, then set the start date to December 31. Otherwise, set the start date to January 1.
- If only the day is missing, if the month/year is earlier than the month/year of the first dose then set the start date to the first day of the month. Otherwise, set the start date to the last day of the month.

Partial end dates will only be imputed if the year is non-missing:

- If the month and day are missing then set the end date to December 31.
- If only the day is missing, then set the end day as the last day of the month.

If the imputed start date is later than the imputed end date then set the imputed start date to the imputed end date.

## 3.11. Visit Windows

It is expected that all visits should occur according to the protocol schedule. However, analysis visits will be derived based on study day for all by-visit summaries and analyses. Analysis visit designations are detailed in [Table 3-1](#).

**Table 3-1 Post-Baseline Analysis Visit Designations**

| Analysis Visit | Analysis Visit Range |
|-----------------------|-----------------------------|
| Day 1                 | Day 1                       |
| Day 2                 | Day 2                       |
| Day 3                 | Days 3-5                    |
| Day 8                 | Days 6-9                    |
| Day 11                | Days 10-12                  |
| Day 15                | Days 13-17                  |
| Day 21                | Days 18-24                  |
| Day 29                | Days 25-33                  |
| Day 45                | Days 34-52                  |
| Day 60                | Days 53-70                  |

In the event there are multiple assessments within a given analysis range, the value closest to the target day (understood to be the day identified in the analysis visit) will be chosen. If more than one measurement are the same distance from the target day, the earlier visit will be chosen.

In data listings, the relative day of all dates will be presented.

### **3.12. Interim Analyses**

No interim analyses are planned for this study.

## **4. STUDY ANALYSES**

### **4.1. Subject Disposition**

Subject disposition will be tabulated by treatment group and include the number randomized, the number treated, the number in each population for analysis, and the number who completed the treatment (who reached Day 14 for SOC alone), the number who completed the study (i.e., reached Day 29 visit), and the number who discontinued treatment and discontinued study and reason(s) for withdrawal.

A by-subject data listing of treatment and study completion information including the reason for treatment discontinuation and study discontinuation, if applicable, will be presented.

### **4.2. Demographics and Baseline Characteristics**

Demographics and baseline characteristics will be tabulated by treatment group. Age (years), race, gender, ethnicity, and smoking status use will be summarized using descriptive statistics. In addition, the number of subjects with Child-Pugh A liver impairment, and the number of patients who received a bacillus Calmette-Guérin (BCG) vaccine will be provided. Baseline disease characteristics will also be summarized; these include the number of subjects in each stratification level (based on disease severity), the number of subjects who require each type of respiratory assistance, the number of subjects who had antibodies to SARS-CoV-2 at baseline, SpO2 at baseline, and days from symptom onset, from PCR positivity, and from start of hospitalization to randomization. Demographic and baseline data for each subject will be provided in data listings.

Medical history will be coded using MedDRA v23.0 and presented by system organ class and preferred term by treatment group. If a subject had more than one medical history event within a system organ class, the subject is counted once for each preferred term and once for the system organ class. Medical history data will also be provided in by-subject listings.

Demographic and baseline characteristics summary tabulations will be produced for the ITT population.

### **4.3. Efficacy Evaluation**

#### **4.3.1. Analysis of the Primary Efficacy Endpoint**

The primary endpoint of time to viral clearance will be analyzed with the log-rank test for treatment difference based on a two-sided alpha-level of 0.10 and summarized using Kaplan-Meier methodology. The time to viral clearance (in days) is defined as the time of Negative or Lower Limit of Quantification (LLOQ) results (without any quantitative results after that) as measured by PCR for SARS-CoV-2 via scheduled nasopharyngeal and oropharyngeal swab samples minus the date of first dose + 1.

Subjects who have no evidence of viral clearance will be censored at the time of the last PCR measurement with the following conditions:

- Patients whose symptoms worsen (defined as an increase of  $\geq 1$  point on the 6-point Ordinal Scale from baseline) on the day of the last PCR measurement, or who die will be censored at Day 29,
- Patients who are lost to follow-up will be censored on the day of the last PCR measurement.

The median time to viral clearance will be estimated based on the Kaplan-Meier estimator; additional summary statistics will be presented, including the 25th and 75th percentiles, 90% CIs (the log-log transformation) on the median and other percentiles and proportion of censored subjects. Viral clearance rates at Days 3, 8, 11, 15, and 29 will also be presented.

The analysis of the primary efficacy endpoint will be done using the ITT population.

The primary analysis will be supplemented with a sensitivity analysis, using a stratified log-rank test, where the treatment difference based on a two-sided alpha-level of 0.10 will be summarized and stratified by disease severity.

The analysis will also be repeated by the dexamethasone usage subgroup, where patients will be categorized as having received dexamethasone if they received it at any time prior to the last viral clearance assessment.

Kaplan-Meier curves will be provided for the overall ITT population. By-subject data listings of viral clearance data will also be provided.

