## **2. SUBJECT POPULATION**

### **2.1. Population Definitions**

The following subject populations will be evaluated and used for presentation and analysis of the data:

- Intent-to-treat (ITT) population – All subjects randomized to treatment. Subjects in the ITT population will be analyzed based on the treatment to which they were randomized, irrespective of what treatment they actually received. This population was selected for the analysis of the primary and secondary endpoints in order to maintain the benefits of randomization and avoid the potential bias associated with the non-random loss of the participant.
- Safety population – All ITT subjects who received either favipiravir + SOC or SOC alone. Subjects in the safety population will be analyzed based on the actual treatment they received, irrespective of the treatment to which they were randomized. It is anticipated that the safety population will be the same as the ITT population.
- Modified intent-to-treat (mITT) – All subjects of the ITT population that have a post-baseline assessment of viral shedding and at least one PCR positive result for SARS-CoV-2 in any protocol-required swab samples. Note that results recorded as less than the lower limit of quantification (LLOQ) are considered to be negative. Subjects in the mITT population will be analyzed based on the treatment to which they were randomized, irrespective of what treatment they actually received.
- Per protocol (PP) population – All mITT subjects who adhere to relevant study procedures (i.e. have no major protocol deviation that would be expected to affect efficacy assessments) and have an outcome assessment.
- PK population (PK) – All subjects in the safety population that have at least one result that can be used in the PK summaries.

The ITT population is the primary population for the analysis of efficacy parameters; the mITT and PP populations will be used for supportive inferences concerning efficacy. The PK population is the primary population for the analysis of PK parameters. The Safety population is the primary population for the analysis of safety endpoints.

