#### **3.2. Efficacy Endpoints and Hypothesis Testing**

The primary efficacy endpoint is time to viral clearance by PCR, measured on Days 1, 3, 8, 11 (while hospitalized); and days 15 and 29 (if able to return to clinic or still hospitalized).

Contrary to what is included in the study protocol, the hierarchical testing of key secondary endpoints will not be performed. For more information please refer to [Section 5](#).

All analyses will be conducted at the two-sided alpha-level of 0.10. P-values for all analyses other than the primary efficacy endpoint will be presented for the purposes of ‘descriptive significance’ only.

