### **3.5. Baseline Definitions**

For all analyses, baseline will be defined as the most recent measurement prior to the first administration of study drug for patients on favipiravir. For patients on SOC, baseline will be defined as the closest (either before or after) measurement to randomization.

For the purpose of time-to-event analyses, treatment start date is used as the origin point for patients on favipiravir, while randomization date is used for patients on SOC.

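### As written, the primary endpoint lets a negative or below-LLOQ Day 1 pre-dose swab, if no quantifiable result follows, count as viral clearance at time 1

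*SAP*

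**What the plan says.** - **Event.** SAP 4.3.1 takes clearance as the time of "Negative or Lower Limit of Quantification (LLOQ) results (without any quantitative results after that"), from scheduled nasopharyngeal and oropharyngeal swabs. Time is that date minus the first-dose date, plus 1.
- **Origin.** SOC subjects have no first dose. SAP 3.5 supplies the origin: "treatment start date is used as the origin point for patients on favipiravir, while randomization date is used for patients on SOC".
- **Swabs.** SAP 3.2: "The primary efficacy endpoint is time to viral clearance by PCR, measured on Days 1, 3, 8, 11 (while hospitalized"), then Days 15 and 29. SAP 1.2.6.1 also lists Day 1 for the primary endpoint. Protocol 7.1 collects that swab pre-dose and lists it ahead of randomization.
- **Population.** "The analysis of the primary efficacy endpoint will be done using the ITT population", that is, all randomized subjects. Protocol 5.1 requires a positive PCR within the previous 72 hours but does not require the Day 1 study swab to be positive.
- **mITT.** SAP 2.1 requires a post-baseline shedding assessment and "at least one PCR positive result for SARS-CoV-2 in any protocol-required swab samples", treats results below LLOQ as negative, and gives this set a supportive role.
- **Censoring.** "Subjects who have no evidence of viral clearance will be censored at the time of the last PCR measurement", except that subjects who die, or whose symptoms worsen on the day of the last PCR, are censored at Day 29.
- **Reporting.** "Viral clearance rates at Days 3, 8, 11, 15, and 29 will also be presented".

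**The concern.** The event definition needs two things: a negative or below-LLOQ scheduled swab, and nothing quantitative after it. A Day 1 pre-dose swab can meet both. The subject then enters the log-rank test as cleared at time 1, on a sample taken before favipiravir could have acted.

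The plan itself foresees such subjects. The mITT definition exists partly to remove randomized subjects with no positive protocol swab. Five secondary time-to-event analyses (clinical recovery, defervescence, cough, dyspnea, NEWS2) carry an explicit entry condition that the subject be abnormal at or near baseline. The primary endpoint carries none.

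Events of this kind hold no information about treatment. Occurring alike in both arms, they dilute the contrast and cost power. This is the one endpoint whose p-value SAP 3.2 does not label descriptive, and protocol 9.1 ties proof of concept to it, with 25 subjects per arm.

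**Working it through.** **1. The literal event time.** With the swab on the date of first dose (favipiravir) or of randomization (SOC), time = 0 + 1 = 1. A swab on the previous calendar date would give 0, so time 1 holds when the two dates coincide.

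**2. The plan's own sample size.** Inputs from SAP 3.1: medians 4 and 11 days, two-sided alpha 0.10, power 90%, 15 days of observation. Exponential clearance is assumed.
- Hazard ratio: 11/4 = 2.75.
- Probability of clearance by 15 days: 1 − 2^(−15/4) = 0.926 and 1 − 2^(−15/11) = 0.611, mean 0.769.
- Freedman events: (1.645 + 1.282)² × (3.75/1.75)² = 39.3. Dividing by the mean probability gives 51.2, so 52 in total. Power at 50 is 0.894.
- The exponential-rate formula gives 25.3 per arm. Schoenfeld gives 34 events and power 0.932 at 50.

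The stated 25 per arm is reproduced to within two subjects in total.

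**3. Effect of the rule.** The share of subjects negative or below LLOQ on Day 1 and never quantifiable later is not in the documents. It is assumed at 2 to 20%, equal in both arms. Simulation: 40,000 trials per cell (Monte Carlo standard error at most 0.23 points), 25 per arm, exponential clearance detected at the next scheduled swab (Days 3, 8, 11, 15, and 29 where stated), study day d taken as d − 1 days elapsed, log-rank test at two-sided 0.10. Power in %:

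| Horizon | Share | Day 1 counted | From Day 3 | Never-quantifiable removed (as in mITT) |
|---|---|---|---|---|
| Day 29 | 0% | 94.8 | 94.8 | 94.8 |
| Day 29 | 2% | 93.7 | 94.0 | 94.5 |
| Day 29 | 5% | 91.6 | 92.4 | 93.9 |
| Day 29 | 10% | 87.7 | 89.6 | 92.8 |
| Day 29 | 20% | 78.5 | 82.5 | 89.6 |
| Day 15 | 0% | 92.2 | 92.2 | 92.2 |
| Day 15 | 2% | 90.6 | 91.0 | 91.7 |
| Day 15 | 5% | 88.1 | 89.2 | 91.1 |
| Day 15 | 10% | 83.5 | 85.7 | 89.6 |
| Day 15 | 20% | 73.5 | 78.0 | 86.0 |

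**4. Splitting the loss at 5/10/20%.**
- Day 1 rule alone (from Day 3 minus Day 1 counted): 0.8/1.9/4.0 points to Day 29; 1.1/2.2/4.5 on the 15-day horizon.
- Total loss against a share of zero: 3.2/7.1/16.3 points to Day 29; 4.1/8.7/18.7 on the 15-day horizon.

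So the Day 1 rule explains about a quarter of the total. The rest arises because never-quantifiable subjects stay in ITT: barred from Day 1, they become events at Day 3, which are nearly as uninformative.

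**5. Type I error.** With both medians at 11 days and shares of 5/10/20%, the rejection rate with Day 1 counted is 0.102/0.101/0.103. From Day 3 it is the same. There is no inflation.

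**6. Sensitivity to missing later swabs.** If half of the never-quantifiable subjects have no later swab and are censored at Day 1, ITT power with Day 1 barred is 93.2/91.1/85.6% at 5/10/20% (to Day 29). The clause then recovers somewhat more than in step 4.

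**The case against.** The best defence is context. Clearance presupposes virus, entry requires a recent positive PCR, and clearance rates are tabulated only from Day 3. All of this points to a post-baseline intent, and a sensible programmer might well apply it. It does not settle the matter: the Day 3 list is a reporting list, not an event rule, and the text that defines the event names no first eligible swab.

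It is also fair to say that the supportive analysis exists already. SAP 2.1 makes mITT supportive for efficacy, and mITT drops exactly these subjects. That stands. What remains is to show that result beside the primary one, since the only sensitivity analysis named in 4.3.1 is the severity-stratified test.

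Several stronger readings are tempting, and the documents do not support them:
- *Every Day 1 negative is an event.* No. A later quantitative result cancels it.
- *The whole fall in power is due to the Day 1 rule.* No. Step 4 shows that most of it comes from keeping never-quantifiable subjects in ITT.
- *The rule favours one arm, because SAP 3.5 defines baseline differently by arm.* SAP 4.3.1 gives one event rule for both arms. For SOC, "For patients on SOC, baseline will be defined as the closest (either before or after) measurement to randomization", so a Day 1 swab taken just after randomization would ordinarily be baseline anyway.
- *The test is anti-conservative.* The simulated type I error stays at about 0.10.

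**Conclusion.** The gap is real and narrow. As written, SAP 4.3.1 scores a pre-dose result as clearance at time 1 when no quantitative result follows, and nothing elsewhere in the plan prevents it. The probable intent is otherwise.

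Counting Day 1 rather than starting at Day 3 costs about 1, 2 and 4 points of power at shares of 5, 10 and 20% with swabs to Day 29, and slightly more on the 15-day horizon. The total loss from never-quantifiable subjects in ITT is about 3, 7 and 16 points to Day 29, and about 4, 9 and 19 on the 15-day horizon. The Day 1 clause does not recover the larger part of it.

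These figures rest on assumed shares that are equal in both arms, exponential clearance at the planned medians, and complete scheduled swabs except in step 6. The validity of the test is not in question. Importance is minor to moderate and depends on a share that the documents do not give.

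**What to change.** 1. Add to SAP 4.3.1: *the Day 1 swab of protocol 7.1 is the baseline swab in both arms and cannot be a clearance event; only swabs taken after it count.* The bare word post-baseline would not be enough, because Table 3-1, headed as post-baseline, itself lists Day 1, and SAP 3.5 defines baseline differently by arm.
2. Handle a subject with no later swab by the existing censoring rules: at the last PCR, which is then Day 1, unless the Day 29 rule for death or worsening applies.
3. Keep ITT primary. Report the mITT log-rank test beside it, so that the effect of never-quantifiable subjects is visible. mITT membership uses post-baseline samples, so it should stay supportive.

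A primary set restricted to subjects quantifiable on Day 1 is not advised. It also drops subjects who are negative on Day 1 but quantifiable later, and its power can fall below that of the present plan: 91.2 v 91.6% with 5% never and 10% later quantifiable, and 85.5 v 87.7% with 10% and 20%.

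The cost is a few sentences in the SAP. No new data are needed and the primary population does not change. The limit is that ITT power improves only by the small amounts given above.

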9.2 Sample size justification

Approximately 50 subjects will be enrolled. The primary endpoint analysis will consist of a log-rank test of the difference in treatment groups in the time to viral clearance. Based on a recent publication:

(https://www.sciencedirect.com/science/article/pii/S2095809920300631?via%3Dihub)

it is assumed that the median time to clearance for favipiravir would be approximately 4 days, and the median time for SOC would likely be approximately 11 days; this latter estimate may in fact be conservative since SOC is not as likely to reduce viral load as well as the control in the above referenced study. Using two-sided alpha of 0.10 and power of 90% (appropriate for a trial to be used as the justification for a confirmatory, fully-powered blinded and randomized Phase 3 study), and a fixed per-subject observation period of 15 days, an approximate sample size of 25 subjects per arm (total size of 50) would be required.

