### **3. GENERAL STATISTICAL METHODS**

#### **3.1. Sample Size Justification**

Approximately 50 subjects will be enrolled. The primary endpoint analysis will consist of a log-rank test of the difference in treatment groups in the time to viral clearance. Based on a recent publication

(<https://www.sciencedirect.com/science/article/pii/S2095809920300631?via%3Dihub>),

it is assumed that the median time to clearance for favipiravir would be approximately 4 days, and the median time for placebo would likely be approximately 11 days. This latter estimate may be conservative since SOC is not as likely to reduce viral load as well as the control in the above referenced study. Using two-sided alpha of 0.10 and power of 90% (appropriate for a trial to be used as the justification for a confirmatory, fully-powered, blinded and randomized Phase 3 study), and a fixed per-subject observation period of 15 days, an approximate sample size of 25 subjects per arm (total size of 50) is required.

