**Table 4-1 Normalization and Alleviation Criteria**

| Parameter         | Criteria   |
|-------------------|--|
| Fever             | $\leq 37.2$ °C   |
| Respiratory Rate  | $\leq 24$ breaths/minute on room air   |
| Oxygen Saturation | SpO 2 > 94% on room air   |
| Cough             | Mild or absent on a subject-reported scale of severe, moderate, mild, absent |

Subjects with no evidence of clinical recovery will be censored at last assessment of the parameter that is not be recovered. The censoring rules as provided in Section 4.3.1 will also be employed. In addition, if a subject achieves TTCR and then discontinues from the study during the 72 hour confirmation period, it will be censored at the discontinuation. If a subject achieves TTCR and then discharge, it will be confirmed as recovered at the time of achieving TTCR.

The difference between treatment groups will be analyzed using a log-rank test at the two-sided alpha level of 0.10, where the p-value will be presented for descriptive purposes (and using a stratified log-rank test by disease severity as a sensitivity analysis).

Analyses of TTCR will be done on the ITT population. Only patients with at least one abnormal result (among the four symptoms listed in Table 4-1) at baseline (or within 72 hours post baseline) will be included in the analysis.

Kaplan-Meier curves will be provided for the overall ITT population. By-subject data listings will also be provided.

In addition, the analysis will be performed with stratification by disease severity.

The analysis will also be repeated by the dexamethasone usage subgroup, where patients will be categorized as having received dexamethasone if they received it at any time prior to the last assessments of normalization and alleviation criteria.

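### SAP 4.3.1 gives a worsened subject who is then lost two censoring dates, and its Day 29 rule lets unequal worsening bias the viral-clearance test in either direction

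*SAP*

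**What the plan says.** The primary endpoint, time to viral clearance by PCR, is "analyzed with the log-rank test for treatment difference based on a two-sided alpha-level of 0.10" in the ITT population (SAP 4.3.1). By default, a subject with no evidence of clearance is censored at the last PCR. Two conditions follow:

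- Subjects who are at least one point worse than baseline on the 6-point scale "on the day of the last PCR measurement, or who die will be censored at Day 29".
- A separate bullet sets another date for those who drop out of contact: "Patients who are lost to follow-up will be censored on the day of the last PCR measurement".

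The SAP does not say which applies when a subject meets both. The only sensitivity analysis of the primary test is a log-rank stratified by severity, and it keeps the same censoring. Protocol 9.6 says only that missing primary data are censored; it has no worsening rule. SAP Section 5 does not list that rule as a change.

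For time to clinical recovery (TTCR), SAP 4.3.2.2 censors at the last assessment of the parameter that has not recovered, then adds: "The censoring rules as provided in Section 4.3.1 will also be employed". SAP 4.3.2.4 repeats that sentence for NEWS2.

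**The concern.** There are two problems in the primary analysis.

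First, the censoring date is undefined for some subjects. In an open-label trial that choice should not be left to programming.

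Second, a living subject held to Day 29 after an earlier last swab counts as at risk and uncleared at every later event time, yet cannot have an event. The trigger is a score built on hospitalisation, oxygen and ventilation, which are care decisions taken with the arm known. Protocol 9.1 presents viral clearance as an unambiguous indicator of antiviral activity and rests proof of concept on its significance. Under this rule, part of the viral comparison can come from a clinical difference.

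A smaller problem is that TTCR and NEWS2 inherit a trigger tied to the day of the last PCR, although neither endpoint uses PCR.

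**Working it through.** **1. The plan's own sample size.** The inputs are "Using two-sided alpha of 0.10 and power of 90" percent (SAP 3.1), a favipiravir median of 4 days ("it is assumed that the median time to clearance for favipiravir would be approximately 4 days", SAP 3.1), a control median of 11 days ("the median time for SOC would likely be approximately 11 days", Protocol 9.2), 15 days of observation and 25 per arm.

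Exponential hazards are λ₁ = ln2/4 = 0.1733 and λ₂ = ln2/11 = 0.0630, a ratio of 2.75; their mean is 0.1181. With φ(λ) = λ²/(1 − e^(−15λ)), φ(λ₁) = 0.03244, φ(λ₂) = 0.00649 and φ(mean) = 0.01682. The Lachin–Foulkes formula gives, per arm,

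n = [1.645·√(2 × 0.01682) + 1.282·√(0.03244 + 0.00649)]² / (0.1733 − 0.0630)² ≈ 25.3.

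That is 50.6 in total, which reproduces the planned 50. The sample size is not in question.

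**2. The two dates.** Swabs are scheduled on Days 1, 3, 8, 11, 15 and 29. For an uncleared subject who is worse at the last swab and is then lost:

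| Last swab | Worsening bullet | Lost-to-follow-up bullet | Gap |
|---|---|---|---|
| Day 3 | Day 29 | Day 3 | 26 days |
| Day 8 | Day 29 | Day 8 | 21 days |
| Day 11 | Day 29 | Day 11 | 18 days |
| Day 15 | Day 29 | Day 15 | 14 days |

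**3. Effect on the test when there is no viral effect.** Simulated trials had 25 per arm, exponential clearance with the same hazard in both arms, detection on the swab days, and a log-rank test at two-sided 0.10, so 5% is nominal in favour of favipiravir. A share of each arm worsens alive and has no later swab. Unless stated, the last swab is on Day 3, 8 or 11 and worsening is independent of clearance. The worsening shares, the share losing swabs and the 8-day median are assumptions; the 11-day median is the plan's control figure. Runs used 3,000 trials per case, or 20,000 to 60,000 for the 11-day cases. Percentages are SOC v favipiravir.

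| Scenario | False positives favouring favipiravir, SAP rule |
|---|---|
| Equal worsening, or last swab on Day 29 | about 5% |
| Last swab Day 15; 20% v 8%, 28% v 8% (median 11) | 6.5%, 7.6% |
| 30% v 10%, 25–50% of worseners lose later swabs | about 7–8% |
| 20% v 10%, all lose later swabs | 9–11% |
| 30% v 15%, all lose later swabs | 12–13% |
| 30% v 10%, all lose later swabs | 14–17% |
| 20% v 8%, 28% v 8%, all lose later swabs (median 11) | 10%, 14.5% |

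Ranges span separate runs. In the partial-loss row, single 3,000-trial runs gave 5.8% (25% lost) and 9.3% (50% lost). Putting every last swab on Day 3 is more extreme: 13% and 22% for the two median-11 pairs. Under the same independence assumption, last-PCR censoring gives 5–6% throughout.

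Few subjects are needed. At 28% v 8%, about 4.5 SOC and 1.3 favipiravir subjects are held. Kaplan–Meier clearance at Day 29 then reads 70% v 80%, when the truth in both arms is 1 − 2^(−29/11) = 84%.

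**4. The other direction.** With true medians of 4 v 11 days and more worsening on favipiravir (20%, against 8% on SOC), power falls from 0.95 to 0.79 under the SAP rule. With last-PCR censoring it is 0.94.

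**The case against.** The strongest reply is that few subjects should be affected. A living subject who scores worse than baseline is, by the scale, in hospital, where swabs are scheduled; the early-termination visit also includes a swab (Protocol 7.5). Protocol 9.6 calls missing efficacy data in hospitalised patients unlikely and places the difficulty in discharged subjects, who score 1. The trigger looks only at the day of the last PCR, so a later swab taken when the subject is no longer worse removes it. This largely stands, and it is why the lower part of the range deserves weight. It does not remove the problem. A subject who is worse on Day 15, goes home on Day 20 and misses Day 29 is still held to Day 29, because the schedule's discharge swab applies only before Day 15.

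A reader might also infer that last-PCR censoring is the unbiased rule and should replace the sponsor's. The documents do not support that; the nominal error in the working comes from assuming that worsening is independent of clearance.

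- If slow clearers worsen more often (30% v 10%, all losing swabs, identical clearance), last-PCR censoring falsely favours SOC in 10–11% of trials and favipiravir in 1–3%. The SAP rule falsely favours favipiravir in 17%.
- If worsened subjects truly do not clear by Day 29, the SAP rule reproduces the complete-data result. With 20% worsening, Day 29 clearance is 74% (truth and SAP rule) against 90% under last-PCR censoring. At 30% v 10%, power is 39% against 13%.

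The SAP does not state which case it assumes, and no planned analysis tests it.

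For TTCR and NEWS2, a reader might see an outright contradiction. The text is better read as a default plus imported exceptions, with p-values that SAP 3.2 makes descriptive. What stands is that the imported trigger was not adapted to those endpoints.

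**Conclusion.** The point holds in this form. SAP 4.3.1 assigns two censoring dates, up to 26 days apart on scheduled swab days, to an uncleared subject who is worse at the last PCR and is then lost. The Day 29 rule keeps living, unswabbed subjects at risk on an open-label score, and no planned analysis varies the censoring.

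A reader might infer that the rule manufactures a favipiravir effect. It does so only if more SOC subjects worsen and then lose swabs. Equal worsening gives no inflation, and the reverse imbalance costs power. The size is therefore a range that starts at nominal: about 5% with equal worsening or a last swab on Day 29; about 7–8% at 30% v 10% worsening when 25–50% of worseners lose later swabs; and about 9–17% from 20% v 10% to 30% v 10% when all do. The direction is secure. The size is not, because the documents give neither worsening nor missed-swab rates, and they suggest that few subjects are affected. Holding deaths at Day 29 is a defensible convention, since a dead subject cannot clear later.

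**What to change.** - In SAP 4.3.1, state that for a living subject loss to follow-up takes precedence over worsening, with censoring at the last PCR. Keep Day 29 for deaths.
- Leave the worsening rule in the primary analysis. Prespecify a sensitivity log-rank and Kaplan–Meier analysis that censors all living uncleared subjects at the last PCR, and report it beside the primary result with the number of subjects per arm whose date differs.
- In SAP 4.3.2.2 and 4.3.2.4, replace the trigger on the day of the last PCR with the last assessment of that endpoint's own parameter.
- Record the worsening rule in SAP Section 5 as an addition to Protocol 9.6.

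The cost is SAP wording and one extra run. Neither rule is unbiased if worsening is related to clearance, so the two results may differ; showing both makes that dependence visible.
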